### 12.2 AGE

To understand any potential differences amongst age groups which may be relevant to this study, the primary and secondary efficacy endpoints will be evaluated for age groupings (to be determined at time of analysis that creates an even dichotomous split) separately with the results side by side and presented in a table for the ITT analysis set. The purpose of this analysis is to assess consistency across the subgroups of age.

### 12.3 PER-PROTOCOL

As stated in previous sections, all secondary endpoint analysis will be reported in both the ITT and PP populations.

Additional subgroup or exploratory analyses may be completed following database lock.

## 13 REPORTING CONVENTIONS

All reporting will meet the standards of BBA SOP BS002 and its associated work instructions. The planned shells of output for the study report is provided in Attachment 2.

### 13.1 OTHER REPORTING CONVENTIONS

- All tables, figures, and data listings will be presented in Portrait Orientation, unless dimensions are such that Landscape orientation would be easier to interpret. Tables, figures, and listings will be presented on a single page whenever possible.
- Each table will have a supporting data listing.
- Legends will be used for all figures with more than one variable or item displayed.
- All date values will be presented as DDMMYY YYYY (e.g., 29AUG2001) format. A four-digit year is preferred for all dates.
- All tables, figures, and data listings will have a version identifier and date/time stamp on the bottom of each page of output. The analysis population will be identified at the top of all tables, figures, and listings.
- The margins of all tables, figures, and listings will be 0.5-1 inch overall.

- The text of tables and listings will be Times New Roman, 8-12 point.
- Unless otherwise specified in this SAP, all categorical variable summaries will include % (n/N) of each category if >2 categories, or most important category if 2 categories.
- Unless otherwise specified in this SAP, all continuous variable summaries will include the mean, standard deviation, N, median, minimum, and maximum.
- Minimum and maximum will be reported with the number of significant figures as was reported on the CRF, while median, mean and standard deviation will be reported with have one more decimal place than the data.
- Percentages will be reported to one decimal place, unless more precision is required for accuracy.
- P-values will be reported to three decimal places with a leading zero (for example, 0.032). Any p-values that are less than 0.001 will be reported as <0.001.

## ATTACHMENT 1. MAJOR PROTOCOL DEVIATIONS EVALUABILITY CHECKLIST

Attached to SAP as a reference.

**THERM**  
an Almirall company

## ATTACHMENT 2. TABLE, FIGURE, AND LISTING SHELLS

Attached to SAP as a reference.

## Appendix 1: Evaluability Checklist for Definition of Deviations (Major vs. Minor)

DEVIATION CATEGORY	DEVIATION SUBCATEGORY	Selected for study? Yes/No	MEETS THE DEFINITION OF MAJOR?	EXCLUDED FROM PER PROTOCOL ANALYSIS?
INFORMED CONSENT		Yes		
Role Responsible for Identification and Tracking: Sponsor Clinical	a. Signed informed consent/assent not available on site	Yes	Y	Y
	b. Wrong informed consent/assent version signed	Yes	Y	Y
Method of Identification: Direct review of each subject's signed ICF	c. Informed consent not signed and/or dated by subject (or parent/Legally Acceptable representative, if applicable)	Yes	Y	Y
	d. Informed consent/assent not signed and/or dated by appropriate site staff.	Yes	Y	N
	e. Informed consent/assent not signed prior or at Visit 1 following any study procedure	Yes	Y	Y
	f. Other informed consent/assent deviations	Yes	Y	
Study Specific Details and Rationale:	
A. Site to contact subject for copy of ICF for files If subject not provided copy of ICF or copy not available, follow instructions for C.
 
B. Assess follow-up and signing of correct version.
 
C. Follow-up and document reason for oversight, inform IRB as required. Counsel site.
 
D. Assess impact with study team.
			
ELIGIBILITY CRITERIA NOT MET	NA	Yes	Yes	

DEVIATION CATEGORY	DEVIATION SUBCATEGORY	Selected for study? Yes/No	MEETS THE DEFINITION OF MAJOR?	EXCLUDED FROM PER PROTOCOL ANALYSIS?
Role Responsible for Identification and Tracking: Sponsor Clinical Method of Identification: Direct review of each subject's source records when able.	All eligibility criteria	Yes	Y	N
Direct review of electronic data file (remote desk monitoring)	Select eligibility criteria not met	N	Y	Y
Study Specific Details and Rationale: All eligibility criteria deviations are to be reviewed for consideration of important status.				
NOT WITHDRAWN AFTER DEVELOPING WITHDRAWAL CRITERIA		Yes		
Role Responsible for Identification and Tracking: Sponsor Clinical Method of Identification: During monitoring visits, review of data.	a. Not withdrawn from study	Yes	Y	Y
	b. Not discontinued from study treatment	Yes	Y	NA
	c. Other deviation of not being withdrawn after developing withdrawal criteria	Yes	Y	NA
Study Specific Details and Rationale: All protocol specified withdrawal criteria should be reviewed to determine the status of "important" and if documentation exists supporting the non-withdrawal of the subject as well as discussions between the investigator and the sponsor.				
EXCLUDED MEDICATION OR DEVICE		Yes		

DEVIATION CATEGORY	DEVIATION SUBCATEGORY	Selected for study? Yes/No	MEETS THE DEFINITION OF MAJOR?	EXCLUDED FROM PER PROTOCOL ANALYSIS?
Role Responsible for Identification and Tracking:  Sponsor Clinical	a. Medication or dose of medication, excluded by the protocol, was administered	Yes	Y	N
	b. Device, excluded by the protocol, was administered (Example: received another device treatment during study conduct)	Yes	Y	Y

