7.8. Prior and Concomitant Medications and Therapies

7.8.1 Permitted

Subjects will be allowed to continue with their usual necessary medical therapies, with no medically unnecessary changes in their diet or overall lifestyle. If medical conditions exist at the start of the study that require drug therapy during the study, those conditions and any concomitant medications prescribed should be recorded in the subject's source documents and the appropriate section of the CRF.

Subjects must abstain from exclusionary procedures/medications/therapies as listed under the Exclusion Criteria for the duration of the study.

Investigational Device: ThermiRF

Protocol No.: Thermi_0005

Version Date: Final 10-May-2016

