#### 3.2 FINAL ANALYSES AND REPORTING

All final, planned, analyses identified in the protocol and in this SAP will be performed only after the last subject has completed the Day 180 follow-up visit. Key statistics and study results will be made available to ThermiGen, LLC following database lock. Any post-hoc, exploratory analyses completed to support planned study analyses, which were not identified in this SAP, will be documented and reported as necessary. Any results from these unplanned analyses will also be clearly identified as post-hoc analyses.

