### 6.2 PER-PROTOCOL POPULATION (PP)

The per-protocol population (PP) for this study will include all subjects who have completed the Day 90 visit, have an evaluable photograph to measure the area of lift from the Day 90 visit, have not used an excluded medication, and do not have a major protocol violation (see Attachment 1).

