## 10 EFFECTIVENESS ANALYSES

The following analyses will be carried out on the ITT and PP populations.

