**Study Specific Details and Rationale:**

All medication deviations should be reviewed to determine if documentation exists supporting the non-withdrawal of the subject as well as discussions between the investigator and the sponsor.

VISIT COMPLETION		Yes		
Role Responsible for Identification and Tracking:  Sponsor Clinical	a. Missed visit at critical data point	Yes	Y	Y
	b. Missed any visit other than critical data point	Yes	Y	N
Method of Identification:  Data review.	c. Out of window visit/phone contact	Yes	N	N

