**Study Specific Details and Rationale:**

A. Missed visits will be reviewed for importance as follows: is there a pattern of non-compliance, was the visit missed due to an AE/SAE, or because of safety management guidance. Multiple missed consecutive visits/phone contact will be assessed. Team will review these categories during reviews and determine importance.

ASSESSMENT OR TIME POINT COMPLETION		Yes		
Role Responsible for Identification and/or Tracking:	a. Missed critical assessment (e.g., Photos for critical timepoint, questionnaires)	Yes	Y	Y
	b. Incomplete assessment	Yes	Y	N
	c. Assessment not properly performed	Yes	Y	N

DEVIATION CATEGORY	DEVIATION SUBCATEGORY	Selected for study? Yes/No	MEETS THE DEFINITION OF MAJOR?	EXCLUDED FROM PER PROTOCOL ANALYSIS?
Sponsor clinical team	d. Out of window assessment ( optional )	Yes	N	N
	e. Out of Window efficacy assessment ( optional )	Yes	Y	N
Method of Identification:	f. Out of Window safety assessment ( optional )	Yes	Y	N
Data review	g. Out of Window treatment administration ( optional )	N/A	Y	N
Study Specific Details and Rationale: Part 1: Overall, assessments will be reviewed to determine if there is a general pattern of non-compliance which may be determined by the team to be Important. Missed VS and physical exam may impact subject safety if changes in these assessments cannot be evaluated. AEs must be assessed to determine safety of IP. Missed efficacy evaluations (i.e., questionnaires) will impact the data analysis and integrity of the study.				
FAILURE TO REPORT SAFETY EVENTS PER PROTOCOL		Yes		
Role Responsible for Identification and Tracking:	a. SAE Occurred but was not reported. SAE warranted subject be discontinued but subject was not discontinued	Yes	Yes	N
Investigator, sponsor clinical team	b. AEs of special interest not reported or not properly qualified by the PI for causality	Yes	No	N
Method of Identification:	c. Pregnancy occurred	Yes	Yes	N
Review of safety reports (spontaneous or voluntary reports)	d. Other: Define: RASH (specific eCRF page)	Yes	Yes	N
Study Specific Details and Rationale:				

**Sponsor:** ThermoGen, LLC.  
**Protocol Number:** Thermo\_0005  
**Protocol:** *An Open-Label, Single-Center, Single-Treatment, Safety and Effectiveness Evaluation of Percutaneous Radiofrequency in Achieving Submental Lift*  
**Version:** Protocol Rev. A; SAP Rev. B

Table 1	
Analysis Populations	
	% (n/N)
All Enrolled	XX

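### The per-protocol set has no cut-off date, so another device treatment after Day 90 removes a valid Day 90 result from the supportive Day 90 response rate

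*SAP*

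**What the plan says.** SAP 6.2 defines a single PP population. Two conditions are tied to the primary time point: subjects must "have completed the Day 90 visit, have an evaluable photograph to measure the area of lift from the Day 90 visit". The other two carry no date: subjects must "have not used an excluded medication, and do not have a major protocol violation (see Attachment 1").

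In the checklist (headed Appendix 1 and cited in SAP 6.2 as Attachment 1), an excluded device counts as major and as a reason for exclusion from PP. The example given is a subject who "received another device treatment during study conduct". Protocol 7.8.1 shows how long that period is: "Subjects must abstain from exclusionary procedures/medications/therapies as listed under the Exclusion Criteria for the duration of the study". The last study visit is Day 180.

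SAP 10 applies this set to every effectiveness analysis: "The following analyses will be carried out on the ITT and PP populations". The SAP shells have one PP row in Table 1 and one PP flag in Listing 1. That set feeds Table 9.1 (Day 90 primary endpoint) and Tables 9.2.1 to 9.2.5 and 9.3, which reach Day 180. SAP 3.2 says the final analyses "will be performed only after the last subject has completed the Day 180 follow-up visit", so later deviations are known when the Day 90 PP rate is computed.

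Excluded medication is also undated in SAP 6.2, which removes such subjects from PP. The checklist row for an excluded medication says they are not removed. These two passages contradict each other.

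**The concern.** Membership of a Day 90 analysis set should depend on what happened up to Day 90. Here it also depends on what a subject does in the following three months, after the Day 90 result exists. In an open-label study, subjects and the investigator see the outcome. A subject disappointed at Day 90 has more reason to have another procedure than one who is pleased. If that happens, the rule takes non-responders out of the Day 90 denominator and leaves responders in, although both complied fully up to the measurement.

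What is at stake is the PP result for the primary endpoint (Table 9.1) and the Day 90 columns of the PP secondary tables. These are supportive results. The primary analysis is on the ITT population.

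**Working it through.** **1. Does the text lead to the removal?** Take a subject with an evaluable Day 90 image and another device treatment at Day 120.
- Day 90 visit and photograph conditions (SAP 6.2): met.
- No major violation (SAP 6.2): not met. The device row applies, and Day 120 falls within study conduct.
- Visit-specific PP set, or a rule limiting the exclusion to data collected after the deviation: none in either document.

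The subject is not in PP and so is absent from Table 9.1.

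**2. The plan's own figure.** Inputs from SAP 5: n = 70, null rate 0.45, 70% response in non-dropouts, 12.5% dropout counted as non-response, one-sided α = 0.05.
- Effective rate: 0.70 × 0.875 = 0.6125.
- Exact critical value: 39 responders, with P(X ≥ 39 | 70, 0.45) = 0.0467.
- Power: P(X ≥ 39 | 70, 0.6125) = 85.8%. This agrees with the stated figure of about 85%.

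**3. Size of the shift.** Assumptions: PP would hold 70 × 0.875 ≈ 61 subjects, and k Day 90 non-responders are removed for a later device treatment. The documents give no value for k. With x responders, the rate is x/(61 − k) and the p-value is P(X ≥ x | 61 − k, 0.45).

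| k | x = 34: rate | p | x = 43 (near the planned 70%): rate | p |
|---|---|---|---|---|
| 0 | 34/61 = 55.7% | 0.060 | 43/61 = 70.5% | <0.001 |
| 2 | 34/59 = 57.6% | 0.035 | 43/59 = 72.9% | <0.001 |
| 4 | 34/57 = 59.6% | 0.019 | 43/57 = 75.4% | <0.001 |

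The count of 34 was chosen because it lies just short of significance at n = 61, where 35 are needed. It shows sensitivity and is not a forecast.

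**4. Effect on the PP test if the true rate is 45%.** Exact enumeration at n = 61, with subjects removed at assumed probabilities:

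| Non-responders removed | Responders removed | Type I error |
|---|---|---|
| 0% | 0% | 3.5% |
| 5% | 0% | 6.1% |
| 10% | 0% | 8.9% |
| 20% | 0% | 17.5% |
| 10% | 5% | 6.1% |
| 10% | 10% | 4.0% |

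Equal removal stays below 5%. The bias comes from the difference in removal between non-responders and responders.

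**5. What ITT shows in the same scenario.** If the other 9 subjects (70 − 61) are dropouts with no Day 60 image to carry forward, ITT is 34/70 = 48.6%, p = 0.314. The available-data ITT analysis is 34/61, p = 0.060. Neither depends on k.

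**The case against.** The strongest case against is that little depends on this set.

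- **The primary analysis is untouched.** ITT keeps each observed Day 90 result whatever happens later. This stands, and it limits the importance of the point.
- **PP is not the only support.** A reader might infer that it is. SAP 7.3 and 10.1 (item 2) prespecify an available-data ITT analysis, shown in Table 7.1, and it keeps every Day 90 image. A gap between it and PP would be visible. This stands.
- **PP would not falsely agree with ITT.** A reader might infer that deletion makes PP echo a favourable ITT result. In the example ITT fails clearly (p = 0.314), so a significant PP would disagree with it. Conversely, ITT succeeds from 39/70. If the 9 subjects outside PP are all non-responders, PP is then at least 39/61 = 63.9%, p = 0.002, before any later removal. This stands under those assumptions.
- **Missed visits after Day 90.** The checklist also excludes for "Missed visit at critical data point" and "Missed critical assessment (e.g., Photos for critical timepoint, questionnaires"). A reader might infer that a missed Day 180 visit counts. Neither document names Day 180 as critical. SAP 6.2 ties its visit and photograph conditions to Day 90, and the checklist does not exclude from PP for missing a non-critical visit. Day 90 is the natural reading, though the term is undefined.
- **Removal rates are assumed.** The device row removes responders too, and no document links further treatment to response. SAP 7.4 also says that major violations may exclude a subject, which leaves some discretion. All true, but discretion exercised with Day 90 results in hand does not replace a cut-off date.

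**Conclusion.** The point holds for deviations that SAP 6.2 and the checklist leave undated. The clear case is another device treatment between Day 90 and Day 180, which removes a valid Day 90 result from Table 9.1 and from the Day 90 PP secondary results. Excluded medication is undated as well, but its status is unsettled because the two passages disagree.

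The direction of the bias rests on non-responders being likelier to have further treatment, which is plausible and undocumented. With an assumed PP set of 61 and 34 responders, two removals raise the rate by 1.9 percentage points (55.7% to 57.6%), enough to cross 0.05 in that borderline case. Near the planned 70% the rate rises by 2.4 points (70.5% to 72.9%) and no test conclusion changes.

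The primary ITT conclusion and the available-data ITT analysis are not affected. This is a worthwhile correction to a supportive analysis and does not threaten the trial's main result.

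**What to change.** - **SAP 6.2:** apply to the Day 90 PP set only deviations dated on or before the Day 90 assessment. Use that set for Table 9.1 and all Day 90 PP results.
- **Day 180:** add a second PP flag that also applies later deviations, and use it for Day 180 results only. Show both sets in Table 1 and Listing 1.
- **Checklist:** state that the critical data point for the Day 90 PP set is Day 90.
- **Excluded medication:** reconcile SAP 6.2 with the checklist row.

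The cost is SAP wording, one more population flag and a date for each deviation. Listing 17 currently shows only a time period, so the date must be recorded. The Day 90 PP rate may come out slightly less favourable. Sample size, study conduct and the ITT analyses do not change. The change should be made before database lock so that it cannot appear driven by results.

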**Study Specific Details and Rationale:**

All medication deviations should be reviewed to determine if documentation exists supporting the non-withdrawal of the subject as well as discussions between the investigator and the sponsor.

VISIT COMPLETION		Yes		
Role Responsible for Identification and Tracking:  Sponsor Clinical	a. Missed visit at critical data point	Yes	Y	Y
	b. Missed any visit other than critical data point	Yes	Y	N
Method of Identification:  Data review.	c. Out of window visit/phone contact	Yes	N	N

**Study Specific Details and Rationale:**

A. Missed visits will be reviewed for importance as follows: is there a pattern of non-compliance, was the visit missed due to an AE/SAE, or because of safety management guidance. Multiple missed consecutive visits/phone contact will be assessed. Team will review these categories during reviews and determine importance.

ASSESSMENT OR TIME POINT COMPLETION		Yes		
Role Responsible for Identification and/or Tracking:	a. Missed critical assessment (e.g., Photos for critical timepoint, questionnaires)	Yes	Y	Y
	b. Incomplete assessment	Yes	Y	N
	c. Assessment not properly performed	Yes	Y	N

DEVIATION CATEGORY	DEVIATION SUBCATEGORY	Selected for study? Yes/No	MEETS THE DEFINITION OF MAJOR?	EXCLUDED FROM PER PROTOCOL ANALYSIS?
Sponsor clinical team	d. Out of window assessment ( optional )	Yes	N	N
	e. Out of Window efficacy assessment ( optional )	Yes	Y	N
Method of Identification:	f. Out of Window safety assessment ( optional )	Yes	Y	N
Data review	g. Out of Window treatment administration ( optional )	N/A	Y	N
Study Specific Details and Rationale: Part 1: Overall, assessments will be reviewed to determine if there is a general pattern of non-compliance which may be determined by the team to be Important. Missed VS and physical exam may impact subject safety if changes in these assessments cannot be evaluated. AEs must be assessed to determine safety of IP. Missed efficacy evaluations (i.e., questionnaires) will impact the data analysis and integrity of the study.				
FAILURE TO REPORT SAFETY EVENTS PER PROTOCOL		Yes		
Role Responsible for Identification and Tracking:	a. SAE Occurred but was not reported. SAE warranted subject be discontinued but subject was not discontinued	Yes	Yes	N
Investigator, sponsor clinical team	b. AEs of special interest not reported or not properly qualified by the PI for causality	Yes	No	N
Method of Identification:	c. Pregnancy occurred	Yes	Yes	N
Review of safety reports (spontaneous or voluntary reports)	d. Other: Define: RASH (specific eCRF page)	Yes	Yes	N
Study Specific Details and Rationale:				

**Sponsor:** ThermoGen, LLC.  
**Protocol Number:** Thermo\_0005  
**Protocol:** *An Open-Label, Single-Center, Single-Treatment, Safety and Effectiveness Evaluation of Percutaneous Radiofrequency in Achieving Submental Lift*  
**Version:** Protocol Rev. A; SAP Rev. B

Table 1	
Analysis Populations	
	% (n/N)
All Enrolled	XX
Intention to Treat Population (ITT)	XX.X (X/XX)
Per Protocol Population (PPP)	XX.X (X/XX)
Safety Population (SAF)	XX.X (X/XX)
Note: Percentages are based on "All Enrolled"	

Listing 1				
Analysis Populations				
Subject ID	Enrolled	ITT	PP	SAF
XX-XXX	Yes/No	Yes/No	Yes/No	Yes/No

**Sponsor:** ThermiGen, LLC.  
**Protocol Number:** Thermi\_0005  
**Protocol:** *An Open-Label, Single-Center, Single-Treatment, Safety and Effectiveness Evaluation of Percutaneous Radiofrequency in Achieving Submental Lift*  
**Version:** Protocol Rev. A; SAP Rev. B

[figure not shown]
Table 2 Subject Accountability ITT Population				
Visit	Eligible N	Missed % (n/N)	Complete % (n/N)	Early Exit % (n/N)
Screening	XXX			
Procedure	XX	XX.X (X/XX)	XX.X (X/XX)	XX.X (X/XX)
Day 30	XX	XX.X (X/XX)	XX.X (X/XX)	XX.X (X/XX)
Day 60	XX	XX.X (X/XX)	XX.X (X/XX)	XX.X (X/XX)
Day 90	XX	XX.X (X/XX)	XX.X (X/XX)	XX.X (X/XX)
Day 180	XX	XX.X (X/XX)	XX.X (X/XX)	XX.X (X/XX)

Note: Percentages are based on the number of subjects in the ITT Population.

Listing 2 Subject Accountability								
Subject ID	Screening Date	Procedure Date	30 Day Visit	60 Day Visit	90 Day Visit	180 Day Visit	Study Exit	Exit Reason
XX-XXX	Date9.	Date9.	Date9.	Date9.	Date9.	Date9.	Date9.	

**Sponsor:** ThermoGen, LLC.  
**Protocol Number:** Thermo\_0005  
**Protocol:** *An Open-Label, Single-Center, Single-Treatment, Safety and Effectiveness Evaluation of Percutaneous Radiofrequency in Achieving Submental Lift*  
**Version:** Protocol Rev. A; SAP Rev. B

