11.3. Analysis Populations

- **Intent-to-Treat (ITT):** The ITT population includes all subjects that meet inclusion/exclusion criteria, have a signed informed consent form, and are enrolled in the study. The primary effectiveness analysis will be on the ITT population.
- **Safety:** The safety population will include all randomized subjects who received at least one treatment.

Investigational Device: ThermiRF

Protocol No.: Thermi_0005

Version Date: Final 10-May-2016

- **Per-Protocol Population (PPP):** The PPP will include all subjects who:

- Completed the Day 90 visit
- Have an evaluable photograph to estimate area of lift from the Day 90 visit
- Have not used an excluded medication

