## 7.4 PROTOCOL VIOLATIONS

Protocol violations will be summarized in the CSR. This summary will include the number and percent of subjects (overall and by site) with each violation type. Major protocol violations that may exclude a subject from the PP analysis population are identified in a study evaluability checklist and are included in Attachment 1.

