### 10.2 SECONDARY EFFECTIVENESS VARIABLES

There will be no imputation of missing data before analyses on the following variables. Subjects with missing data for a given variable will be excluded from analysis on that variable.

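### The SAP's deviation checklist removes subjects with a valid Day 90 image from the per-protocol lift test for a missed questionnaire, a condition that protocol 11.3 does not contain

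*SAP*

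**What the plan says.** Protocol 11.3 sets three conditions for the PP population: "Completed the Day 90 visit", "Have an evaluable photograph to estimate area of lift from the Day 90 visit" and "Have not used an excluded medication". Questionnaires and major deviations are not mentioned.

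SAP 6.2 repeats these and adds a fourth. Subjects must "have not used an excluded medication, and do not have a major protocol violation (see Attachment 1"). Attachment 1 is the evaluability checklist. Under assessment or time point completion, row a reads "Missed critical assessment (e.g., Photos for critical timepoint, questionnaires") and is marked as selected for the study, major, and excluded from PP. The rationale below that block says "Missed efficacy evaluations (i.e., questionnaires) will impact the data analysis and integrity of the study", so the reference to questionnaires is deliberate. The row ties a critical timepoint to photographs and names no visit for questionnaires.

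Protocol 11.5.1 determines responders from the change in area on Vectra XT 3D images. SAP 10 carries the primary endpoint analysis out in both ITT and PP, and Table 9.1 gives the PP result its own p-value. For the questionnaires themselves, SAP 10.2 says "Subjects with missing data for a given variable will be excluded from analysis on that variable".

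**The concern.** Take a subject who attended Day 90, has an evaluable 3D image and used no excluded medication, but missed a questionnaire. The protocol puts this subject in PP and the SAP takes the subject out. The missing form says nothing about whether lift was measured properly, and two of the four instruments (P-GAIS and P-GSQ) are completed by the physician rather than the subject. Because no visit is named, a missed Day 180 form could, as the row is worded, remove a valid Day 90 lift measurement.

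Two things are at stake. The PP test is run on a different set from the one the protocol defines. And if completing the forms is related to the result, the PP response rate shifts in a single-arm comparison with a fixed 45%.

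**Working it through.** **The plan's own figure.** SAP 5 and protocol 11.2 give N = 70, a null rate of 45%, a 70% response among non-dropouts, 12.5% dropout counted as non-response, and one-sided α = 0.05. The effective rate is 0.70 × (1 − 0.125) = 0.6125. The exact binomial test needs at least 39 responders of 70. Its attained level is 0.0467 and its power 0.858, which agrees with the SAP's approximate 85%.

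**Size of the PP set.** 70 × 0.875 = 61.25, so I take 61 subjects with a Day 90 image. This is an assumption derived from the planned dropout.

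**How many leave PP.** There are four forms (P-GAIS, S-GAIS, P-GSQ, S-GSQ). Let each be missing with probability q, which is assumed.
- Forms always missing together: loss = q.
- Forms missing independently, with any one blank form triggering row a: loss = 1 − (1 − q)⁴.

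| q | Together | Independent |
|---|---|---|
| 2% | 2% (about 1 of 61) | 7.8% (about 5) |
| 3% | 3% (about 2) | 11.5% (about 7) |
| 5% | 5% (about 3) | 18.5% (about 11) |

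**Effect on the PP test when the true rate is 45%.** Let m_N and m_R be the assumed probabilities that row a removes a non-responder and a responder.
- Retained fraction: k = 0.45(1 − m_R) + 0.55(1 − m_N).
- Expected PP rate: 0.45(1 − m_R)/k.
- Rejection probability: the exact one-sided test at 45%, averaged over a PP size distributed as Binomial(61, k).

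With 15% of non-responders and 5% of responders removed, k = 0.4275 + 0.4675 = 0.895 and the rate is 0.4275/0.895 = 47.8%. With those rates reversed, k = 0.3825 + 0.5225 = 0.905 and the rate is 0.3825/0.905 = 42.3%.

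| Missing, non-responders / responders | Expected PP rate | PP rejection probability |
|---|---|---|
| No exclusion (n = 61) | 45.0% | 0.035 |
| 11.5% / 11.5% | 45.0% | 0.039 |
| 4% / 2% | 45.5% | 0.048 |
| 15% / 5% | 47.8% | 0.089 |
| 5% / 15% | 42.3% | 0.015 |

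Equal missingness moves 0.035 to 0.039 without any bias. The exact test's attained level depends on n, and PP size now varies. Part of the rise to 0.048 at 4%/2% has the same cause.

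**Sensitivity near the threshold.** 34/61 gives one-sided p = 0.060. Removing one non-responder leaves 34/60, with p = 0.046.

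**Under the planning assumptions.** Without the exclusion, PP is about 43/61 = 70.5%. If six subjects are removed, the rate is 43/55 = 78.2% when all are non-responders, 39/55 = 70.9% when removal is proportional, and 37/55 = 67.3% when all are responders. Power at a 70% rate is about 98% or more at n = 61, 58, 55 and 52, so loss of power is not the issue.

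**The case against.** The strongest reply is that little depends on this. The primary inference is on ITT. SAP 7.3 and 10.1 (item 2) also plan an analysis of subjects with available data, which drops only those with neither a Day 90 nor a Day 60 image. A subject with a Day 90 image and a blank form stays in both. That stands. A reader might infer that valid data are lost from the primary analysis, or that the trial's type I error is inflated; the documents support neither, since the loss is confined to PP and success is not defined on PP.

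A reader might also infer that the exclusion favours the device. That requires non-responders to miss forms more often than responders, and the documents give no evidence either way. The forms are scheduled at the same visit as the Day 90 images, so 15% missing among imaged subjects is a stress case. The independent-forms loss is an upper case too. Row a does not say that one blank form of four is enough, and row b (incomplete assessment) does not exclude from PP.

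Finally, a SAP may refine a PP definition, one PP set serves all endpoints, and SAP 7.4 is permissive: "Major protocol violations that may exclude a subject from the PP analysis population are identified in a study evaluability checklist". Adding major-deviation criteria is ordinary practice. But row a itself marks exclusion as yes, and its rationale concerns data integrity in general rather than lift. If discretion is intended, PP membership is not fixed in advance in an open-label study. It could be argued that a missed Day 90 form means the visit was not completed; the protocol does not say so, and that reading cannot cover Day 180 forms.

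**Conclusion.** The conflict is real but narrow. As written, the SAP removes from Table 9.1 subjects whom protocol 11.3 keeps and whose lift was validly measured, and it does so for a gap that SAP 10.2 already handles. The ITT primary and available-data results do not change.

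The size is uncertain. With 2% to 5% missing per form, the loss from PP is 2% to 5% if forms go missing together and 7.8% to 18.5% in the independent, any-blank-form case. The PP rate can move up, down or not at all. The rejection probabilities in the table rest on 61 imaged subjects, a true rate of 45% and assumed missingness. The definitional mismatch does not depend on any of these assumptions.

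**What to change.** Split row a of the assessment block in Attachment 1. A missed Day 90 3D photograph stays excluded from PP. A missed questionnaire becomes not excluded from PP and is left to SAP 10.2. Add a sentence to SAP 6.2 that PP membership for the Table 9.x analyses does not depend on questionnaire completion at any visit.

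The cost is one checklist row and one sentence, with no new data. Questionnaire denominators in the PP tables may then differ slightly from the PP lift denominator; the titles of Tables 9.2.1 to 9.2.4 already limit those tables to available data. The change removes the questionnaire conflict with protocol 11.3 only. The other major-violation criteria that the SAP adds, such as those on consent and excluded devices, remain.
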